# 9.1.4 Lost to Follow-up

For subjects whose status is unclear because they fail to appear for study visits without stating an intention to discontinue or withdraw, the investigator must show "due diligence" by documenting in the source documents steps taken to contact the subject, e.g., dates of telephone calls, registered letters, etc. A subject should not be considered as lost to follow-up until due diligence has been completed or until the EOS.

# 9.1.5 Early Study Termination by the Sponsor

The study can be terminated by ITB-MED at any time. Should this be necessary, the subject should be seen as soon as possible and treated as a prematurely withdrawn subject. The Investigator may be informed of additional procedures to be followed in order to ensure that adequate consideration is given to the protection of the subject's interests. The Investigator will be responsible for informing IRBs and/or ECs of the early termination of the trial.

# 9.2 Study Completion

Study completion is defined as when the last subject finishes their final study visit (Month 12) and any repeat assessments associated with this visit have been documented and followed-up appropriately by the Investigator or, in the event of an early study termination decision, the date of that decision.

Each subject will be required to complete the study in its entirety and thereafter no further study treatment will be made available to them (as applicable based on local regulations). Subjects who are prematurely withdrawn from the study should be treated according to local SoC per the Investigator's judgment. The study will complete when the last subject completes their Study Completion Visit, and any repeat assessments associated with this visit have been documented and followed-up appropriately by the Investigator.

#### 9.3 Subject Replacement

### Replacement during Dose Escalation

Subjects will not be replaced on study. However, if a subject is considered as non-evaluable, enrollment of a new subject to the current cohort will be considered if there is less than the required number of evaluable subjects. Enrollment of new subjects may be considered until at least the minimum number (4) or at most the maximum number (8) of evaluable subjects is achieved within the cohort.

Minimum and maximum numbers of evaluable subjects per cohort are defined in the guidelines for dose escalation and determination section.

### 10 Safety Monitoring and Reporting

### 10.1 **Definition of Adverse Events and Reporting Requirements**

#### 10.1.1 **Adverse Events**

The Investigator is responsible for reporting all AEs that are observed or reported during the study, regardless of their relationship to study medication or their clinical significance. Given the potential for protracted time between a subject providing informed consent and organ transplant, AE collection will commence once a subject has provided consent and has at least one invasive study procedure completed and/or performed (e.g., blood draw).

An AE is any untoward medical occurrence in a study subject administered an investigational product which does not necessarily have a causal relationship with the product. An AE can therefore be any unfavorable and unintended sign (including a new, clinical important abnormal laboratory finding), symptom, or disease, temporally associated with the product, whether or not related to the product.

Pre-existing diseases or conditions will not be considered an AE unless there is an increase in the frequency or severity, or a change in the quality of the disease or condition (worsening of a pre-existing condition is considered an AE).

The occurrence of AEs must be sought by non-directive questioning of the subject at each visit during the study. AEs also may be detected when they are volunteered by the subject during or between visits or through physical examination findings, laboratory test findings, or other assessments.

Page 75 of 117 Protocol TCD601B102 (2.0) Confidential

AEs must be recorded under the signs, symptoms, or diagnosis associated with them, and accompanied by the following information: Assessment and grade according to the CTCAE criteria (version 5.0 or higher)

• Relationship to the study treatment

If the event is due to lack of efficacy or progression of underlying illness (i.e., progression of the study indication) the assessment of causality will usually be 'Not suspected.' The rationale for this guidance is that the symptoms of a lack of efficacy or progression of underlying illness are not caused by the trial drug, they happen in spite of its administration and/or both lack of efficacy and progression of underlying disease can only be evaluated meaningfully by an analysis of cohorts, not on a single subject

- Duration (start and end dates) or if the event is ongoing, an outcome of not recovered/not resolved
- Whether it constitutes a SAE and which seriousness criteria have been met
- Action taken regarding with study treatment
- Outcome

AEs (including lab abnormalities that constitute AEs) should be described using a diagnosis whenever possible, rather than individual underlying signs and symptoms.

AE monitoring should be continued for the duration of the study; in the event a subject does not complete the study for any reason, AE monitoring should continue for 6 months after the last administration of investigational product.

Once an AE is detected, it must be followed until its resolution or until it is judged to be permanent (e.g., continuing at the EOS), and assessment must be made at each visit (or more frequently, if necessary) of any changes in severity, the suspected relationship to the interventions required to treat it, and the outcome.

Information about adverse drug reactions for the investigational drug can be found in the IB.

Abnormal laboratory values or test results constitute AEs only if they are considered clinically significant and/or require therapy or active management.

#### 10.1.2 **Serious Adverse Events**

A Serious Adverse Event (SAE) is any untoward medical occurrence that:

- Results in death
- Is life-threatening
  - O Note: The term "life-threatening" in the definition of 'serious" refers to an event in which the subject was at risk of death at the time of the event; it does not refer to an event which hypothetically might have caused death if it were more severe.
- Results in persistent or significant disability/incapacity
- Constitutes a congenital anomaly/birth defect

- Requires inpatient hospitalization or prolongation of existing hospitalization
  - O Note: Inpatient hospitalization is defined as 24 hours in a hospital or an overnight stay. An elective hospital admission to treat a condition present before exposure to the study drug, or a hospital admission for a diagnostic evaluation of an AE, does not qualify the condition or event as an SAE. Further, an overnight stay in the hospital that is only due to transportation, organization, or accommodation problems and without medical background does not need to be considered an SAE. Routine treatment or monitoring of the studied indication, not associated with any deterioration in condition that has not worsened since the signing of consent is not considered an SAE.
- Is an important medical event

All reports of intentional misuse and abuse of the product are also considered SAEs irrespective if a clinical event has occurred.

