# 2 Objectives and Endpoints

Table 2-1 Objectives and Related Endpoints

Objective(s)	Endpoint(s)	
Primary Objective	Endpoints for primary objective	
To assess the safety, tolerability, PK and PD of siplizumab compared to rATG, in de novo renal transplant recipients at 12 months post-transplant.	
 
Adverse events
 
Serious adverse events
 
Clinically significant changes in clinical chemistry, hematology, vital signs, serology
 
siplizumab PK
 
Immunophenotyping
 
CD2 RO
 
eGFR via MDRD
 
	

 
Secondary Objectives
 
To measure changes in peripheral lymphocyte immunophenotype
 
To measure the time-course and duration of siplizumab induced lymphocyte depletion and time to recovery
 
To measure peripheral CD2-receptor occupancy following siplizumab administration over time
 
To assess the incidence of treated biopsy proven acute rejection (tBPAR) at 12 months
 
To assess the incidence of treatment emergent de novo, donor specific antibodies (DSA) at 12 months
 
To assess the incidence of antibody meditated rejection at 12 months
 
To assess repail function via eGER using MDRD equation at
 
	
 
Endpoints for secondary objectives
 
Immunophenotyping via FACS
 
Lymphocyte counts
 
CD2 RO
 
Anti-siplizumab Ab
 
Incidence of BPAR
 
de novo-DSA / anti-HLA antibody measurement
 
incidence of AMR
 
	

 
To assess renal function via eGFR using MDRD equation at Months 3, 6, 12 or EOS
 
		

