#### 8.4.7 **Renal Biopsy**

Any biopsies performed according to local practice must be recorded. Biopsies will be read by the local pathologist according to local practice and the 2017 Banff criteria (Appendix 7). The results of the biopsy read by the local pathologist will be listed on the applicable eCRF.

Additionally, for all suspected rejection episodes, regardless of initiation of anti-rejection treatment, a renal biopsy must be performed within 48 hrs. The results will be used for subject management for acute rejection.

Please refer to the Laboratory Manual for details on biopsy handling and histology assessments.

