### 12.4 **Analysis of the Primary Endpoint(s)**

#### 12.4.1 **Definition of Primary Endpoint(s)**

All safety data, including laboratory assessments, vital signs and AEs are considered primary endpoints.

All information obtained on AEs will be displayed by treatment and subject. The number and percentage of subjects with AEs will be tabulated by body system and preferred term with a breakdown by treatment arm. A subject with multiple AEs within a body system is only counted once towards the total of this body system. No formal statistical analysis will be done for the safety and tolerability evaluation.

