#### **10.1.2. Adverse Events**

Each AE and SAE term will be recorded as a verbatim term on the case report forms (CRFs). All AEs and SAEs will be coded by primary system organ class (SOC) and mapped to a preferred term using the MedDRA dictionary (version 26.0 or higher). The investigator will assess AE severity and relationship to the study treatment.

All AEs will be listed. However, only treatment emergent adverse events (TEAEs) will be included in the AE summaries. A TEAE is defined as any AE with an onset date on or after the first study treatment dosing date. In addition, any AEs that the investigators deem to be treatment related, regardless of onset date, will also be considered TEAEs and will be included in the AE summaries.

For the purpose of calculating treatment emergence and inclusion in summary tables, incomplete onset dates will be imputed using the method described in Appendix A.

AEs will be summarized by the number and percentage of subjects in each primary SOC and preferred term. Subjects will be counted only once for each primary SOC and each preferred term. Summary tables of AEs by primary SOC, preferred term and severity will be provided. If a subject has more than one AE coded to the same preferred term, the subject will be counted only once for that preferred term by using the event with the highest severity. Similarly, if a subject has more than one AE within a primary SOC category, the subject will be counted only once in that SOC category by using the event with the highest severity. AEs by primary SOC, preferred term and relationship to study drug will be provided as well. If a subject has more than one AE coded to the same preferred term, the subject will be counted only once for that preferred term by using the most related event. Similarly, if a subject has more than one AE within a primary SOC category, the subject will be counted only once in that primary SOC category by using the most related event. In addition, serious adverse events (SAEs) by primary SOC and preferred term will be provided. Deaths and SAEs will be summarized similarly to AEs. All adverse event tables will also include the total number of events, counting multiple events per subject.

In the AE summary, preferred terms within each SOC will appear in alphabetical order.

Frequencies for deaths and hospitalizations will also be summarized by treatment group and overall.

All information obtained on AEs will be displayed by treatment group.

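### The SAE definition lets an unplanned admission to work up an adverse event be recorded as non-serious

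*Protocol*

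**What the plan says.** Protocol 10.1.2 lists as a seriousness criterion an event that "Requires inpatient hospitalization or prolongation of existing hospitalization", and defines inpatient as 24 hours in hospital or an overnight stay. The note under that criterion contains four exemptions:

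- "An elective hospital admission to treat a condition present before exposure to the study drug";
- admission for diagnostic work-up, where "a hospital admission for a diagnostic evaluation of an AE, does not qualify the condition or event as an SAE";
- overnight stays for transport, organizational or accommodation reasons;
- routine treatment or monitoring of the studied indication without deterioration.

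The other seriousness criteria, including "Is an important medical event", are untouched by the note.

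Table 2-1 (Protocol 2) lists SAEs as an endpoint for the primary objective, next to AEs. Protocol 12.7 says AE and SAE rates are monitored continuously to support early discontinuation of an arm. Protocol 10.1.4 requires SAEs to be reported within 24 hours and applies the same procedure to AEs of special interest regardless of seriousness. SAP 10.1.2 adds: "Frequencies for deaths and hospitalizations will also be summarized by treatment group and overall".

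**The concern.** The word elective governs only the first exemption, for conditions that predate exposure. The diagnostic exemption has no such limit, so on its wording it covers unplanned admissions as well. The other exemptions already deal with logistical stays and with monitoring without deterioration. What this one adds is the removal of admissions prompted by a new adverse event.

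In renal transplantation, an overnight admission to investigate a creatinine rise or a fever is an event a safety reviewer would expect to find among the SAEs. Under this note it can be recorded as non-serious. It is then missing from the SAE tables and SAE-rate monitoring, and it cannot be handled as a suspected unexpected serious reaction.

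The trial is open-label, and Protocol 4 acknowledges investigator bias. Whether an admission was for diagnosis or for treatment is a judgment made with knowledge of the arm. The protocol gives no rule for an admission that begins as one and becomes the other.

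**Working it through.** The documents give no figure behind this definition, so there is nothing to reproduce. The check has two parts: following each type of work-up admission through the reporting rules, and the arithmetic of an arm of 8.

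**Which admissions fall through.** In each case, assume the admission is unplanned and no other seriousness criterion is met.

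- *Suspected rejection or creatinine rise.* Protocol 8.4.7 says that for all suspected rejection episodes "a renal biopsy must be performed within 48 hrs". Rejection is not among the events of special interest in Protocol 10.1.3. Protocol 6.7.1 requires rejection episodes to be entered on their own eCRF, but entry within 24 hours is a preference only. If the biopsy is negative, the event is not a treated biopsy-proven rejection either (Protocol 8.4.8, SAP 11.5). It then appears only as a non-serious AE. Protocol 4.5.1.4 shows why this type matters: an AKI-like syndrome occurred in 9 of 10 patients in two earlier siplizumab studies, with biopsies negative for T-cell mediated rejection. Those patients also received conditioning and donor marrow, and the protocol says renal dysfunction was not reported in other populations. The syndrome is nevertheless a named reason for discontinuation (Protocol 9.1.2), and it is not an event of special interest.
- *Non-opportunistic infection.* The relevant special-interest entry in Protocol 10.1.3 covers infections only if they are serious. It therefore depends on the definition in question and is no independent safeguard.
- *Opportunistic infection (EBV, CMV, BK) and malignancy including PTLD.* These are events of special interest regardless of seriousness, so 24-hour reporting is kept. A PTLD work-up that is never confirmed and has no EBV finding is not clearly covered.
- *Prolongation of the transplant stay for a work-up.* The exemption speaks of admissions, so on its wording it does not reach prolongations.

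**Scale.** Inputs: 8 subjects per siplizumab arm (Protocol 12.9), and Clopper-Pearson two-sided 95% intervals for binomial variables (SAP 8).

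Change in an arm's SAE incidence per subject whose only SAE is reclassified: 1/8 = 12.5 percentage points.

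Interval limits for x of n: lower = Beta⁻¹(0.025; x, n−x+1), upper = Beta⁻¹(0.975; x+1, n−x), with lower = 0 when x = 0. For n = 8:

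| Subjects with an SAE | Incidence | 95% interval |
|---|---|---|
| 0 | 0% | 0 to 36.9% |
| 1 | 12.5% | 0.3 to 52.7% |
| 2 | 25.0% | 3.2 to 65.1% |

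One reclassified subject moves the arm up one row of this table. At 1 of 8 the interval is 52.7 − 0.3 = 52.4 points wide, so a shift of 12.5 points is visible in a descriptive table but small against the uncertainty already present.

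**The case against.** The strongest reply is that nothing is lost, only relabelled. Protocol 12.4.1 states: "All safety data, including laboratory assessments, vital signs and AEs are considered primary endpoints". A reclassified event is still graded, followed, listed and tabulated by severity. Important medical event remains open as a route to seriousness, and graft loss is always an SAE (Protocol 8.4.9). Rejection has its own eCRF, near real-time review by the sponsor and the DMC (Protocol 9.1.1) and its own analysis (SAP 11.5). If a work-up leads to inpatient treatment, the note does not exempt the treatment stay. Protocol 8.4.7 requires a biopsy, not an admission. Detailed SAE instructions are in a Site Study Manual that is not available here.

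All of this stands, and it rules out several stronger readings that a reader might infer:

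- *That these events drop out of the primary endpoint.* They move from the SAE count to the AE count, and both belong to the primary safety data.
- *That PTLD and infections in general lose 24-hour reporting.* The special-interest rule keeps it for PTLD and opportunistic infections.
- *That a stopping decision could be missed.* The rules in Protocol 9.1.1 use death, graft loss, PTLD, toxicity grade and Banff grade, not SAE status.
- *That the SAP's hospitalization and SAE tables contradict each other.* SAP 10.1.2 does not define which admissions count, so they may differ, but no contradiction is shown.
- *That the loss is unequal between arms.* Open-label judgment makes this possible; the documents give neither direction nor size.

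The reply does not close the gap for events whose only seriousness criterion is the admission. The important-medical-event route is again investigator judgment, and a work-up with a negative result has no separate capture as a rejection.

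**Conclusion.** The concern holds in a narrow form. Followed as written, Protocol 10.1.2 takes an unplanned work-up admission out of the SAE endpoint, out of SAE-rate monitoring and, unless the event is of special interest, out of 24-hour reporting. The practical gap is suspected rejection or AKI-like events and non-opportunistic infections.

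Its size is 12.5 points of SAE incidence per affected subject in an arm of 8. This assumes the subject has no other SAE in 12 months and that the investigator does not use another criterion. How many subjects would be affected cannot be derived from the documents. No sample size, error rate or test is involved, because the analysis is descriptive (Protocol 12.4.2, SAP 8.0).

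One further use is sensitive to the definition: Protocol 12.4.2 foresees historical controls for AE and SAE incidence. If those sources apply no such exclusion (an assumption), the SAE comparison would not be like for like. Overall this is a cheap improvement to a reporting definition and no threat to the trial's conclusions.

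**What to change.** In Protocol 10.1.2, limit the diagnostic exemption to planned (elective) admissions. State that an unplanned admission prompted by an AE meets the hospitalization criterion, and that a work-up admission which becomes inpatient treatment does too. Deleting the exemption altogether would go too far, because a planned overnight investigation of a minor AE would then become an SAE. Carry the wording into the eCRF guidelines and the Site Study Manual.

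In SAP 10.1.2, state which admissions the hospitalization summary counts, and reconcile that summary with the SAE listing, so that any admission not classed as an SAE is shown with its reason.

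The cost is a short protocol change, a sentence or two in the SAP, a few more SAE reports and a slightly higher SAE rate. No dose, sample size or clinical procedure changes.

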### 10.1.3 Adverse Events of Special Interest

The following AEs are selected as adverse events of special interest (AESI) for surveillance and follow-up, both serious and non-serious, based on previous experience with siplizumab, all:

- Serious Infections
- Opportunistic Infections, including EBV, CMV, BK virus
- Malignancies, including LPD/PTLD

# 10.1.4 SAE Reporting

Every SAE, regardless of causality occurring after the subject has provided informed consent and had at least one invasive study procedure performed and continuing until the final study visit, must be reported to the ITB-MED Safety Department or its designee. Reporting must take place within 24 hours of learning of its occurrence and is done by entering the SAE into the eCRF within 24 hours of awareness. Additionally, all AESI whether serious or not should also be reported following the same procedure.

Recurrent episodes, complications, or progression of the initial SAE must be reported as follow-up to the original episode, regardless of when the event occurs. This information must be submitted within 24 hours of the Investigator receiving the follow-up information. An SAE that is considered completely unrelated to a previously reported one should be reported separately as a new event.

Information on all SAEs (either initial or follow up) is collected and entered in the eCRF(s). Information may also be submitted in writing to when important information or clinical updates are required that may not be feasible to provide within the eCRFs. Please refer to the Site Study Manual for detailed instructions on the reporting of SAEs.

If the SAE is not previously documented in the IB or Package Insert (new occurrence) and is thought to be related to the study treatment, ITB-MED Safety may urgently require further information from the investigator for health authority reporting. ITB-MED may need to inform all investigators involved in any study with the same study treatment that this SAE has been reported.

Suspected Unexpected Series Adverse Reactions (SUSARs) will be collected and reported to the competent authorities and relevant ethics committees in accordance with EU Guidance 2011/C 172/01 or as per national regulatory requirements in participating countries.

Any SAEs experienced after the Month 12 (EOS) visit should only be reported to ITB-MED Safety if the investigator suspects a causal relationship to study treatment. For subjects who terminate from the study prematurely, SAEs should only be reported if they occur within 6 months following the last administration of study treatment and a causal relationship is suspected.

